6.3 Adverse Effects and Precautions

The subjects will be counseled concerning what to expect during the procedure and the importance of communicating any problems to the investigator. All device-related AEs occurring in this study will be recorded in the Case Report Forms. Each AE will be assessed for its probable cause (unrelated to the treatment, device related, procedure related, etc).

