2.2 Safety

Safety of ExAblate will be determined by an evaluation of the incidence and severity of device related complications from the first treatment day visit through the 3-Months post-treatment time point.

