2.4 Study End Points

Safety

A full safety profile will be developed for the ExAblate treatment of bone metastases. All adverse events will be captured and summarized as defined in **Section-6.2**. Adverse events (type, frequency, severity) are expected to be similar to those captured for the original PMA study (PMA # P110039).

For his study, the Safety comparison with the data of the Pivotal (IDE Study G070022) study will be descriptive with no statistical endpoints.

Efficacy

A full efficacy profile will be developed for the ExAblate treatment of bone metastases. For this study efficacy will be determined by comparing outcomes at the 3 month visit to baseline within subjects. Additionally the safety and efficacy of treatment Responders and Non-Responders will be tabulated, and compared with that of the original PMA (P110039).

The primary endpoint is the proportion of responders at the 3 month study visit.

Definition of terms:

- Patient Responders: these are all ExAblate treated patients who experience at least a 2 point improvement from baseline on NRS at the treated site without increase in medications
- Patient Non-Responders: these are all ExAblate treated patients who experience less than 2 points improvement from baseline to 3 months on the NRS at the treated site without increase of medication or increased medications.
- Patient Pain Progression: these are all ExAblate treated patients who either experience 2 points worsening from baseline to 3 months on the NRS at the treated site or who increase morphine equivalence 25% or more. Pain progression is a subset of non-responders.

Secondary Endpoints

This study has two secondary end points. The goal of these secondary end points is to assess the impact of the ExAblate treatment of painful bone Mets on the overall quality of life and clinical benefits to ExAblate MRgFUS treated patients:

Quality of life outcomes of all treated patients will be captured during the course of the study. A comparison between baseline and 3 months post-ExAblate treatment of the BPI-QoL will be performed.

Pain Medications of all patients will be captured and summarized. Changes in narcotic medications will be expressed in morphine equivalents.

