4.4 Follow-up

The follow-up visits of all patients will be completed at 1 week and 1, 2 and 3 months post-ExAblate treatment. Patients will be evaluated for general health, efficacy measurements as well as for device/procedure related AEs that may have occurred during the follow-up period. Additional data regarding dosage and frequency of analgesic intake for the management of the

metastatic bone tumor induced pain will also be collected. Following treatment the study staff will mark the treatment NRS form indicating the place where the treatment was performed. These marked questionnaires will be provided to the patient to complete by the study staff for each time point in the follow up. The patient will be instructed to indicate the change of pain at the place of treatment. Although the 1-Week, 1-Month, 2-Month and 3-Month visits are office visits, and in view of the patient population general health may change at any given time due to the underlying cancer disease, participating sites may use their discretion to make the visit(s) a phone visit to accommodate the patient best interest. However, all attempts should be made to ensure an office visit. The visits will be used to evaluate the patient's NRS, BPI-QoL, and KPS, pain medication intake, symptoms and their general health, including any safety related issues and any changes in symptoms following treatment. For phone visits, study personnel will contact the patient, inquire about AEs and question the patient according to the pain questionnaire, and pain medication intake, and fill it out in parallel. Because the KPS is a physician completed assessment it may not be required for visits completed by telephone. The study personnel will then sign and date the completed forms.

All pre-treatment and post treatment MR and CT images will be de-identified and archived, and then will be forwarded to the Sponsor

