5 STATISTICAL ANALYSIS PLAN

This study is a designed as a single arm within subjects comparison of outcomes at the 3 month visit to baseline. For this study, a total of 70 patients meeting approved

commercial guidelines for bone metastases will be enrolled and treated with the ExAblate system at from 7 to 10 investigational sites.

Safety

A full safety profile will be developed for the ExAblate treatment of bone metastases. All adverse events will be captured and summarized as defined in **Section-6.2**. Adverse events (type, frequency, severity) are expected to be similar to those captured for the original PMA study (PMA # P110039). For this study, the Safety comparison will be descriptive with no statistical endpoints.

Efficacy

A full efficacy profile will be developed for the ExAblate treatment of bone metastases. For this study efficacy will be determined by comparing outcomes at the 3 month visit to baseline within subjects. Also, the outcomes will be compared with the original efficacy data of the PMA (P110039), where the proportion of treatment Responders and Non-Responders will be tabulated and compared.

The statistical hypothesis is that the proportion of responders will be significantly greater than the proportion of subjects experiencing pain progression (worsened pain or increased pain medications usage) by at least 30% or an odds ratio of at least 2.

Secondary Endpoints

Medications use and quality of life will be analyzed as secondary endpoints.

PATIENT GENERAL HEALTH STATUS

Patient overall quality of life status will be assessed by the BPI-QoL Pain Interference scale which will be administered pre-treatment and post-treatment. The trajectory of change may be analyzed descriptively by regression slopes.

BASELINE DATA ANALYSES

Baseline clinical, demographic and patient reported outcome characteristics will be tabulated and compared descriptively to the original PMA.

HEALTH COST AND SERVICES UTILIZATION

Summary tabulations and figures may be developed for reimbursement purposes only.

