6.2 Anticipated Treatment Side Effects From ExAblate

Based on previous treatment experience, the following anticipated side effects have been identified as possible treatment related complications of ExAblate treatment. These can be classified into Non-significant and Significant Anticipated Treatment Side Effects based on their medical severity, additional treatment required and long term consequences for the patient. All Treatment Side Effects will be reported in the Case Report Forms for the study and included in the final study analysis.

Non-significant Anticipated Treatment Side Effects of ExAblate treatment are those, which normally resolve without sequelae within 10-14 days of the treatment:

- Transient fever
- Oral temperature $>100.4^{\circ}\text{F}/38^{\circ}\text{C}$
- Pain in the area of treatment.
- Transient pain in the skin.
- Swelling or firmness in the treated area

- Minor (1° or 2°) skin burns less than 2 cm in diameter
- Bruising in the treatment area

Significant Anticipated Treatment Side Effects of ExAblate are those which may require medical treatment, may have sequelae, and for which time of resolution is not defined:

- Necrosis of tissue outside the targeted volume due to heat conduction from heated bone.
- Nerve damage, or loss of sensation in the area other than the treatment area.
- Hemorrhage in the treated area requiring emergency treatment.
- Skin burns with ulceration of the skin.
- Skin retraction, and scar formation..
- Complications of conscious sedation (Cardiac, Pulmonary, Drug reactions)

The table below summarizes all the potential risks to a patient from ExAblate treatment and the time course when they would most likely be observed.

Immediate (up to 48 hrs post treatment)	Mid term (up to one month)	Long term (more than one month)
Pain in the treatment area.	Pain in the area of treatment	Pain in the area of treatment
Skin burns	Swelling or firmness in the treated area	Nerve damage or loss of sensation in the treated or neighboring areas
Necrosis of normal tissue resulting from incorrect targeting	Nerve damage or loss of sensation in the treated or neighboring areas	Scar formation from skin burn.
Risks of conscious sedation including reaction to drugs and over sedation.	Fever as reaction to treated tissue.	
Adverse reactions to Gadolinium DTPA		

Transient pain in skin or back	Ulceration of skin or scar formation from skin burn.	
Bleeding in the treatment area.		

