6.5 Adverse Event Reporting

It is the responsibility of the investigator to document all treatment related and device related Adverse Events (AE's), which occur during the course of the study. At each visit, the investigator will evaluate AE's. AE's not previously documented in the study will be recorded on the Adverse Event Log within the subject's CRF. The nature of each event, date and time (when appropriate) of onset, outcome, frequency, maximum intensity, action taken, and attribution will be recorded. AEs already documented in the CRF (i.e., at a previous assessment) and designated as 'ongoing', should be reviewed at subsequent visits as necessary. If these have resolved, the documentation in the CRF should be completed including an end date for the event. If an AE increases in frequency or severity during a study period, a new record of the event will be started.

Standard Code of Federal Regulation (CFR) definitions for Serious Adverse Events (SAEs) will be used for evaluation of adverse events.

SAE [§803.3(aa)(1)] is an injury or illness that:

causes death

- *is life threatening, even if temporary in nature;*
- *results in permanent impairment of a body function or permanent damage to a body structure; or*
- *necessitates medical or surgical intervention to preclude permanent impairment of a body function or permanent damage to a body structure.*

All AE's (related or unrelated) meeting the criteria for an SAE require notification of the sponsor and the reviewing IRB as soon as possible, with subsequent completion of additional paperwork provided by the sponsor fully documenting the course of the event, all treatments, and final outcome. Initial reporting of an SAE should be made to the sponsor no later than two (2) working days after the PI learns of the incident.

Standard Code of Federal Regulation (CFR) definitions for Unanticipated Adverse Device Effects (UADEs) will be used for evaluation of this type of adverse event.

UADE [§812.3(s)] means any serious adverse event on health or safety or any life-threatening problem or death caused by, or associated with, a device, if that effect, problem, or death was not previously identified in nature, severity, or degree of incidence in the investigational plan or application (including a supplementary plan or application), or any other unanticipated serious problem associated with a device that relates to the rights, safety, or welfare of subjects.

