Any UADEs will be reported to the Sponsor and to the reviewing IRB as soon as possible. However, in no event must this report be made later than two (2) working days after the PI learns of the incident.

Other common non-study or non-device related, minor health complaints will not be collected as AE's (for example: colds, sprains, headaches). Patients who have a progression of their primary disease or symptoms that lead to an alternative treatment will not be reported as an AE.

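### The plan promises a summary of all adverse events, but its collection rules conflict on whether non-serious unrelated events and treated-site pain are recorded

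*Combined protocol and SAP*

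**What the plan says.** **Reporting.** Section 5 states that "A full safety profile will be developed for the ExAblate treatment of bone metastases". Sections 2.4 and 5 both say that "All adverse events will be captured and summarized as defined in" Section 6.2, and both expect the type, frequency and severity of events to resemble those in the original PMA study. The comparison is descriptive. Section 2.2 sets a narrower objective: "incidence and severity of device related complications from the first treatment day visit through the 3-Months post-treatment time point".

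**Collection.** Section 4.4 has patients evaluated at follow-up for "device/procedure related AEs that may have occurred during the follow-up period". Section 6.3 says "All device-related AEs occurring in this study will be recorded in the Case Report Forms". Section 6.5 opens by making the investigator responsible to "document all treatment related and device related Adverse Events".

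**Exclusions.** Section 6.5 ends with two. Common minor complaints unrelated to the study or device are not collected. Progression of the primary disease is also left out, as are "symptoms that lead to an alternative treatment will not be reported as an AE".

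**Treated-site pain.** Section 6.2 lists "Pain in the area of treatment" as an anticipated side effect. It says that all treatment side effects go on the case report forms and into the final analysis.

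**The concern.** Safety is one of the two stated purposes of this post-approval study (Sections 4.1 and 5.2). A table of all adverse events is only as complete as the rule that decides what enters the database. If a site reads Sections 4.4, 6.3 and the opening of 6.5 as the operative rule, relatedness is judged before recording. The study has one arm, so the people making that judgement know that every patient was treated. A non-serious event that they call unrelated may leave no record, and nobody can revisit the attribution. A site that works from the other sentences in the same sections would record the same event.

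The progression exclusion adds a second gap. Pain at the target lesion is the symptom under treatment and also a listed side effect of the treatment. When it worsens and the patient moves to another therapy, one section makes it reportable and another can be read as removing it.

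**Working it through.** The plan gives no figure on this point, and the safety comparison has no alpha, power or margin. The check therefore sets the passages side by side.

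**Step 1. Scope of collection.**

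| Place | Scope implied |
|---|---|
| Sections 2.4 and 5 | All adverse events |
| Section 2.2 | Device-related complications, treatment day to 3 months |
| Section 4.4 | Device- or procedure-related events |
| Section 6.3, recording sentence | Device-related events |
| Section 6.3, attribution sentence | Each event assessed for cause, with unrelated as one category |
| Section 6.5, opening | Treatment- and device-related events |
| Section 6.5, log sentence | Any event not already documented, with no relatedness limit; attribution recorded |
| Section 6.5, serious events | Related and unrelated |
| Section 6.1, fractures | All, with relationship assessed afterwards |

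The rows do not reduce to one rule. Serious events and fractures are safe under any reading. Events judged related are covered too, although the three related-event rules differ among device, procedure and treatment. What remains uncertain is the non-serious event judged unrelated that is neither a fracture nor a common minor complaint.

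**Step 2. The cross-reference.** Sections 2.4 and 5 send the reader to Section 6.2 for how events are captured and summarised. That section lists anticipated side effects and their likely timing. It sets no scope for adverse event collection. The recording rules stand in Section 6.5.

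**Step 3. Treated-site pain.** The risk table in Section 6.2 lists pain at the treated area in all three windows: up to 48 hours, up to one month, and beyond one month. The progression exclusion in Section 6.5 speaks of the primary disease or symptoms and has no exception for the treated site. A flare that leads to another therapy can thus be classed either way.

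**Step 4. Would another route catch it?**
- *Serious event reporting.* The criteria in Section 6.5 are death, threat to life, permanent impairment or damage, or intervention to prevent these. A pain flare leading to another therapy would usually meet none of them.
- *Efficacy data.* Section 2.4 counts a 2-point worsening at the treated site, or a rise of 25% or more in morphine equivalents, as pain progression. This works while the patient stays in follow-up. Section 6.4 lets patients leave to pursue other treatment. After an exit, the observed-data analysis has no 3-month value, and the carry-forward rule in Section 5.3 uses the previous visit, which may predate the flare.

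Both routes can therefore miss the same patient.

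**The case against.** The strongest reply is that the protocol does not confine recording to related events. The Section 6.3 sentence says that device-related events are recorded; it does not say that others are not. The next sentence provides for an unrelated category, the log sentence has no relatedness limit, and attribution is already a recorded item. Excluding common minor unrelated complaints would be redundant if all unrelated events were out of scope. All of this stands, and it rules out the inference that only related events are recorded. It does not remove the conflict, because three separate instructions still state the duty in terms of related events.

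Four other strong readings may tempt a reader, and the documents do not support them:

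- *The safety profile cannot be produced.* The device-related profile of Section 2.2, serious events and fractures can all be reported.
- *The worst treated-site pain is bound to be lost.* Section 6.5 does not name the treated site, Section 6.2 makes pain there reportable, and efficacy data capture worsening in patients who stay. Loss is possible, not certain.
- *Contrast headaches are lost because headache is an example of an uncollected complaint.* That exclusion covers minor complaints unrelated to the study or device. Contrast imaging is a protocol step (Section 4.3), and Section 6.2 lists gadolinium reactions among the treatment risks.
- *The comparison with the pivotal study is biased toward safety.* That study's collection rule is not given, so neither the existence nor the direction of a bias can be shown.

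The case report forms (Appendix C) are not reproduced and might settle what sites actually enter. Even so, the protocol text should agree with them.

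**Conclusion.** The concern holds as a conflict in collection scope. Two gaps follow. Non-serious events judged unrelated may be recorded differently from site to site, with no later chance to re-attribute those left out. Treated-site pain that leads to another therapy may be missing from the adverse event tables and, if the patient exits, from the efficacy data as well.

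The size cannot be estimated, because the documents give no rate for either kind of event. The setting makes the inconsistency worth removing: 70 patients at 7 to 10 sites, with the last enrolment projected for month 105 (Section 5.4). Events left unrecorded over that period would be hard to recover at the end.

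The conclusion rests on two assumptions: that sites follow the protocol text, and that the case report forms do not already impose a single wider scope. The second gap also depends on reading symptom progression in Section 6.5 to include pain at the treated site. That reading is natural, but it is an inference. The change should be made, though the point does not invalidate the safety objective in Section 2.2.

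**What to change.** 1. Reconcile Sections 2.4, 4.4, 5, 6.3 and 6.5 to one collection scope that matches the promise of all adverse events, from the treatment day to 3 months. The exclusion of common minor unrelated complaints may stay if wanted, provided the safety summary states it.
2. Record relatedness as a field on every entry, so that it does not act as a condition for entry.
3. Tabulate all recorded adverse events and device- or procedure-related events separately.
4. State in Section 6.5 that the progression exclusion does not apply to pain or other events at the treated site.
5. Point the cross-reference in Sections 2.4 and 5 to Section 6.5 in place of Section 6.2.

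The cost is protocol wording and somewhat more adverse event entry, which will be felt in a population this ill. No visits are added, because Section 6.5 already has the investigator evaluate adverse events at each visit.

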6.4 Criteria for Removal from the Study

Subjects can be exited from the study at any time if in the opinion of the principal investigator it is not in the best interest of the patient to carry on as planned. In Addition, patient may also chose to exit the study to pursue other alternative treatment options.

6.5 Adverse Event Reporting

It is the responsibility of the investigator to document all treatment related and device related Adverse Events (AE's), which occur during the course of the study. At each visit, the investigator will evaluate AE's. AE's not previously documented in the study will be recorded on the Adverse Event Log within the subject's CRF. The nature of each event, date and time (when appropriate) of onset, outcome, frequency, maximum intensity, action taken, and attribution will be recorded. AEs already documented in the CRF (i.e., at a previous assessment) and designated as 'ongoing', should be reviewed at subsequent visits as necessary. If these have resolved, the documentation in the CRF should be completed including an end date for the event. If an AE increases in frequency or severity during a study period, a new record of the event will be started.

Standard Code of Federal Regulation (CFR) definitions for Serious Adverse Events (SAEs) will be used for evaluation of adverse events.

SAE [§803.3(aa)(1)] is an injury or illness that:

causes death

- *is life threatening, even if temporary in nature;*
- *results in permanent impairment of a body function or permanent damage to a body structure; or*
- *necessitates medical or surgical intervention to preclude permanent impairment of a body function or permanent damage to a body structure.*

All AE's (related or unrelated) meeting the criteria for an SAE require notification of the sponsor and the reviewing IRB as soon as possible, with subsequent completion of additional paperwork provided by the sponsor fully documenting the course of the event, all treatments, and final outcome. Initial reporting of an SAE should be made to the sponsor no later than two (2) working days after the PI learns of the incident.

Standard Code of Federal Regulation (CFR) definitions for Unanticipated Adverse Device Effects (UADEs) will be used for evaluation of this type of adverse event.

UADE [§812.3(s)] means any serious adverse event on health or safety or any life-threatening problem or death caused by, or associated with, a device, if that effect, problem, or death was not previously identified in nature, severity, or degree of incidence in the investigational plan or application (including a supplementary plan or application), or any other unanticipated serious problem associated with a device that relates to the rights, safety, or welfare of subjects.

Any UADEs will be reported to the Sponsor and to the reviewing IRB as soon as possible. However, in no event must this report be made later than two (2) working days after the PI learns of the incident.

Other common non-study or non-device related, minor health complaints will not be collected as AE's (for example: colds, sprains, headaches). Patients who have a progression of their primary disease or symptoms that lead to an alternative treatment will not be reported as an AE.

